#### 8.2. Inclusion Criteria

- Aged 18 years or over
- Willing and able to give informed consent
- Worked up for EBV therapy in the local COPD clinic

#### Cohort A – No evidence of CV and eligible for EBV treatment

MDT and patient decision for EBV therapy

### Cohort B – Ineligible for EBV treatment following current standard assessments

MDT decision not for EBV therapy

#### 8.3. Exclusion Criteria

- Pregnant, lactating or planning pregnancy during the course of the study
- Inability to lie flat for imaging

Protocol IRAS ID: 346681
HypErpolarised Xenon PuLmonary MRI in the Evaluation for EndobronChial Lung REC Ref:

- Contraindications to MRI examinations as locally determined
- Any other reason, as determined by the study investigators, that renders the participant ineligible for the study

#### 9. PROTOCOL PROCEDURES

#### 9.1. Recruitment

Participants for all cohorts will be recruited from local COPD specialist clinics in Oxford University Hospitals NHS Foundation Trust once identified by a respiratory specialist.

### 9.2. Screening and Eligibility Assessment

Patients will be identified at the COPD MDT by clinicians with the guidance of the research team if they are present at the MDT meeting. Patients will be assessed by the clinical teams for eligibility against the inclusion and exclusion criteria. The clinicians involved in the MDT and the patients clinical care will inform the potential patients of the study and, if they agree, will provide them with the PIS and consent form, and ask their permission to be contacted by the research team to further discuss the study. If they agree to be contacted, a member of the research team will contact them, explain the study, assess eligibility and complete the informed consent form with the patient if they wish to participate. There will be no access to patient identifiable data outside of the direct care team prior to consent.

Participants must satisfy all the approved inclusion and exclusion criteria of the protocol. Participants will receive the Patient Information Sheet via email, in person or by post. They will then be invited to participate, and informed consent will be obtained prior to baseline visit, remotely..

#### 9.3. Informed Consent

The participant must personally sign and date the latest approved version of the Informed Consent form before any study specific procedures are performed.

Written and verbal versions of the Participant Information and Informed Consent will be presented to the participants detailing no less than: the exact nature of the study; what it will involve for the participant; the implications and constraints of the protocol; the known side effects and any risks involved in taking part. It will be clearly stated that the participant is free to withdraw from the study at any time for any reason without prejudice to future care, without affecting their legal rights, and with no obligation to give the reason for withdrawal.

The participant will be allowed as much time as needed to consider the information, and the opportunity to question the Investigator(s), their GP or other independent parties to decide whether they will participate in the study. Written Informed Consent will then be obtained by means of participant-dated signature and dated signature of the person who presented and obtained the Informed Consent. The person who obtained the consent must be suitably qualified and experienced and have been authorised to do so by the Chief/Principal Investigator. A copy of the

Protocol IRAS ID: 346681
HypErpolarised Xenon PuLmonary MRI in the Evaluation for EndobronChial Lung REC Ref:

signed Informed Consent will be given to the participant. Copies of the consent form will be retained at the study site and will be stored with the participant hospital record.

#### 9.4. Randomisation

This study is not randomised. At registration, all participants will be assigned a unique study ID.

#### 9.5. Blinding and code-breaking

There is no blinding in the study and no code breaking procedure.

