### 3. SYNOPSIS

In this study, we aim to identify and characterise the pattern of ventilation in 2 groups of patients with COPD using hyperpolarised xenon-129 MRI (HPX-MRI): A) patients who have been selected and subsequently undergone lung volume reduction therapy using endobronchial valves (EBV), B) those who have been identified as not eligible for endobronchial lung volume reduction therapy using current selection criteria. We also aim to assess and describe the physiological changes following endobronchial lung volume reduction therapy.

Study Title	Hyp E rpolarised X enon P u L monary MR I in the Evaluation for Endobron C hial Lung Volume Reduct I on T herapy (EXPLICIT)			
Internal ref. no. / short title	EXPLICIT			
Study registration	This study will be re	gistered on the ISRCTN		
Sponsor	Oxford University Hospitals NHS Foundation Trust [name] . Email: [contact]			
Funder	Medical Research Cou	uncil (MRC)		
Study Design	Feasibility/pilot			
Study Participants	Up to 40 patients			
Sample Size	Cohort A – up to 20 patients Cohort B – up to 20 patients			
Planned Study Period	Up to 24 months			
Planned Recruitment period	Aug 2025 – Feb 2027			
	Objectives Outcome Measures Timepoint(s)			
Primary	To characterise the pattern of ventilation on HPX-MRI in those with confirmed CV	Quantitative and/or qualitative detection of differences in the pattern of ventilation in the two cohorts being investigated:	Baseline and follow-up	

Protocol

IRAS ID: 346681 REC Ref:

HypErpolarised Xenon PuLmonary MRI in the Evaluation for EndobronChial Lung

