**Volume Reduction Therapy** 

	and those treated with EBV	,	Those with and without confirmed CV; Those who were and weren't successfully treated with EBV.	
Secondary	To describe the physiological changes of the lungs seen on HPX-MRI post-EBV treatment	a)	Quantitative and/or qualitative differences of HPX-MRI findings pre- and post-EBV therapy	Baseline and follow-up
Intervention(s)	Not applicable			
Comparator	Not applicable			_

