#### 7. STUDY DESIGN

This is a prospective, observational, cohort study comprising two patient cohorts – Cohort A – COPD patients, patients selected and planned for EBV treatment and Cohort B – COPD patients deemed unsuitable for EBV treatment due to presence of CV determined by the current gold standard assessments. The comparison of patterns of ventilation and/or physiological movement of gas using HPX-MRI will allow the assessment of collateral ventilation in the two cohorts of patients.

The study will recruit patients into the two cohorts through the local hospital-based COPD clinics. Participants who have been worked up for EBV therapy and their cases discussed at the local COPD multi-disciplinary team (MDT) meeting will be identified by the Clinician and informed of the study. COPD MDT comprises of respiratory physician(s), thoracic surgeon(s), thoracic radiologist(s), specialist nurse(s), respiratory physiotherapist(s) and occupational therapist(s).

The research team may participate in the MDT meetings where possible and may highlight potential patients suitable for the study to the clinicians. The clinicians involved in the MDT and the patients clinical care will inform the potential patients of the study and, if they agree, will provide them with the PIS and consent form, and ask their permission to be contacted by the research team to further discuss the study. If they agree to be contacted, a member of the research team will contact them, explain the study, assess eligibility and complete the informed consent form with the patient if they wish to participate. They will then invite them to undertake their baseline study visit locally at the Churchill Hospital, Oxford University Hospitals NHS Foundation Trust.

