# Visit 2 (6 months follow-up following EBV treatment (Cohort A) or the baseline visit (Cohort B))

Participants will be invited to attend for follow up where all assessments from visit 1 will be repeated.

Face to face visits will take approximately 2 hours.

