#### 11.2. Description of the Statistical Methods

All baseline characteristics and measures will be summarised overall and by cohort and group, using appropriate summary statistics.

ProtocolIRAS ID: 346681HypErpolarised Xenon PuLmonary MRI in the Evaluation for EndobronChial LungREC Ref:

Volume Reduction Therapy CI: [name]

We will aim to describe the prevalence of DV in patients with COPD being worked up for EBV. We will aim to describe the patterns of ventilation seen on HPX-MRI in patients with COPD who have been successfully treated with EBV and compare these findings with those who have not been successfully treated with EBV and those who have not been treated with EBV.

We will aim to examine the relationship between the presence of DV on HPX-MRI and EBV treatment success. We will also aim to correlate the presence of DV seen on HPX-MRI to the presence of CV following Chartis assessment and FC <95% on StratX. Where possible, we aim to examine the relevance of MRI perfusion to the success of EBV treatment and presence of DV. We will also aim to describe the physiological changes observed on HPX-MRI in those who have undergone EBV treatment and whether these changes are different in those who have been treated successfully to those who have not.

Continuous data, including questionnaire outcomes, will be summarised by group and time point using mean and standard deviation (or median and interquartile range if non normally distributed). Effects on outcomes over time (baseline visit and follow up visit) will be analysed using appropriate statistical models.

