#### 12.3. **Data Recording and Record Keeping**

All study data will be stored using one or more of: password protected hard drives and NHS servers in anonymised form.

All documents containing personal data (the linkage spreadsheet and informed consent forms) will be stored securely in lockable cabinets and are only accessible by study staff and authorised personnel. Personal data such as personal addresses, postcodes, emails or telephone numbers of participants will be recorded electronically on spreadsheets for screened and enrolled patients that are accessed via an access-restricted computer. Personal data such as contact details and information that could lead to the identification of a participant (except for those who have consented to be approached for future research) will be destroyed as soon as it is practical to do so and no later than 12 months after the end of the study.

The study investigators are responsible for keeping documents encrypted where possible and kept securely to ensure that in case of an emergency, participants can be identified and contacted. Study data, including all standard of care EBV work up and follow-up taken from the medical notes, will be recorded in a de-identified manner directly into the study database; participants would not be identifiable from this. All participants will be identified by a code number (unique study ID number) on case report forms and any electronic databases. All source documents will have all identifiers removed and replaced by only the unique study ID number. This also applies to control participants.

The consent forms which link the study ID with the name of the participant will be stored in the Trial Master File, separately to the study data, and will be archived for a minimum of 5 years after the end of the study.

Pseudonymised imaging and study data will be transferred and stored on secure OUH NHS FT and servers and/or encrypted hard drives. This transfer will be performed in line with the Trust's information security handling rules Information Protection Policy (ouh.nhs.uk).

Pseudonymised imaging and study data may be used for commercial purposes, but only with consent from a participant.

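### HPX-MRI may be read with knowledge of cohort, StratX, Chartis or EBV outcome, and the baseline scan is not named as the primary one

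*Protocol*

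**What the plan says.** **Reading of the scans**

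- Section 9.5: "There is no blinding in the study and no code breaking procedure". No other section says that HPX-MRI is read without knowledge of cohort, StratX, Chartis or EBV outcome. Section 11.1 says that no separate SAP is in use.
- Section 3, primary outcome: "Quantitative and/or qualitative detection of differences in the pattern of ventilation in the two cohorts being investigated". A reader's judgement can therefore count as the primary result.
- Section 7: "The research team may participate in the MDT meetings where possible". Cases worked up for EBV are discussed there.
- Section 11.2 relates delayed ventilation (DV) on HPX-MRI to Chartis, to StratX and to EBV success.
- Section 12.3: "All participants will be identified by a code number (unique study ID number"). The means to mask a read already exist.

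**Which scan is primary**

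- Section 3 gives the primary timepoints as "Baseline and follow-up". Contrast (a) is with v without confirmed CV. Contrast (b) is "Those who were and weren't successfully treated with EBV".
- Section 9.7 defines the second visit as "Visit 2 (6 months follow-up following EBV treatment (Cohort A) or the baseline visit (Cohort B"), and Appendix A schedules xenon MRI at that visit for all cohorts.
- Section 11.2 plans to describe patterns in the successfully treated and "compare these findings with those who have not been successfully treated with EBV and those who have not been treated with EBV". It names no scan timepoint for this or for the DV analyses.
- Section 11.4 admits everyone with completed HPX-MRI scans and does not restrict the analysis to scans taken before valves.

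**The concern.** The study asks whether HPX-MRI can detect CV and help to predict who benefits from EBV. That makes HPX-MRI the index test, with Chartis and StratX as the reference and EBV success as the outcome. If the person scoring a scan knows the reference result or the outcome, doubtful images tend to be called in the expected direction, and agreement is inflated. The study being observational and open does not require this: patients and clinicians can know everything while the images are scored under a code.

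The timepoint problem is separate. A scan taken six months after valve placement shows the effect of the valves as well as whatever pattern was there before. The secondary objective, which is to describe changes after EBV, rests on that expectation. If such scans feed the primary contrasts, a cohort difference could reflect treatment rather than CV.

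**Working it through.** **Inputs from the protocol.** 20 participants per cohort and DV in more than half of patients with severe COPD (Section 11.3). Its own figure reproduces: 0.50 × 40 = 20, the stated minimum number with DV/CV. The protocol gives no power calculation, names no test for the DV comparison (Section 11.2) and fixes no alpha (Section 11.6).

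**Assumptions made here.** Two-sided Fisher exact test at 0.05; true DV 50% in both cohorts, so any rejection is false; reader knowledge lowers the DV rate in Cohort A and raises it in Cohort B by the same d points.

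**Formula.** The rejection probability is the sum of Bin(a; 20, pA) × Bin(b; 20, pB) over all pairs (a, b) with Fisher p < 0.05, where pA = 0.50 − d and pB = 0.50 + d.

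| Shift each way (d) | DV read in A v B | Gap | Rejection probability |
|---|---|---|---|
| 0 | 50% v 50% | 0 | 2.0% |
| 5 points | 45% v 55% | 10 | 4.7% |
| 10 points | 40% v 60% | 20 | 14.3% |
| 15 points | 35% v 65% | 30 | 33.7% |
| 20 points | 30% v 70% | 40 | 59.9% |

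A shift of 5 points more than doubles the base rate but leaves it under the nominal 5%. The problem becomes material from about 10 points each way, which is a 20-point gap between cohorts.

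**Follow-up scans.** Suppose DV is 50% in both cohorts at baseline and the valves abolish it in a share s of affected Cohort A participants. Follow-up DV in Cohort A is then 0.50 × (1 − s), against 50% in Cohort B.

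| s (assumed) | DV at follow-up, A v B | Rejection probability |
|---|---|---|
| 25% | 37.5% v 50% | 6.7% |
| 50% | 25% v 50% | 26.9% |
| 84% | 8% v 50% | 80.6% |

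The 84% is borrowed as an upper end from the share of treated patients reaching the lung volume target quoted in Section 5. The protocol does not say that DV resolves in that share.

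**Limits.** Both tables describe the cohort contrast. Section 8.1 places inconclusive or incomplete Chartis assessments in Cohort B, so 20 v 20 is not exactly CV v no CV. Contrast (b) divides at most 20 Cohort A participants, and neither table applies to it. For (b) the argument is one of logic: Section 8.1 lets success rest on atelectasis, on lung function or on symptoms, alone or together. A follow-up image that shows the atelectasis is then partly compared with itself.

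**The case against.** **On blinding.** Section 9.5 follows the section on randomisation and is paired with code-breaking, so it may have only allocation in mind. No section names the readers or says that those who attend the MDT also score scans. An automated quantitative measure would be much less exposed. These points stand as limits: bias is permitted, not shown. They do not remove the gap, because the qualitative option is open and nothing in the protocol protects it.

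**On timepoint.** EBV success is known only after treatment, so contrast (b) needs follow-up data whichever scan is used, and the timepoint cell may simply record that. The lay summary speaks of predicting success, post-valve change has its own secondary objective, and Sections 11.2 and 11.7 work by time point. Nothing pools scans from before and after the valves. A reader might infer that post-valve scans are certain to enter the primary comparison. That is the natural reading of the synopsis but not the only one; what can be said is that baseline is not named as primary.

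**Two further inferences to avoid.** One is that neither problem could be put right later. Imaging is stored pseudonymised (Section 12.3) and electronic files are archived (Section 20), so masked re-reading and restriction to baseline remain possible, although as post hoc choices. The other is that atelectasis alone defines success, which would make contrast (b) wholly circular. It is one of three routes, so the circularity is partial.

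**On size.** This is an exploratory pilot with mainly descriptive aims, and it commits to no Fisher test. The percentages therefore illustrate direction and scale; they are not error rates of the planned analysis.

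**Conclusion.** The concern holds as two linked gaps. First, the protocol declares no blinding and does not exempt HPX-MRI readers, while a qualitative read may decide the primary outcome. Second, it lists that outcome at both timepoints without naming the pre-valve scan as primary. Followed as written, it permits informed reads, a CV contrast mixed with treated v untreated, and a partly circular success contrast.

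The first gap is plain in the text. The second is an ambiguity and is held with less certainty. The size of any reader bias is unknown: in the illustration false rejection runs from 4.7% at 5 points each way to 59.9% at 20 points, against 2.0% with none, under an assumed test, alpha and 50% DV rate. The protocol should be amended because the remedy is cheap and serves its own aim of predicting EBV success. The sample size is unaffected.

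**What to change.** **Section 9.5.** Add: *Baseline HPX-MRI will be scored under study ID only, by the existing readers, who will not be given cohort, StratX, Chartis or EBV outcome. Scores will be locked before linkage to these data. EBV success will be classified without sight of the HPX-MRI scores. Any unmasked reads made to find or define a pattern will be labelled exploratory.*

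**Sections 3 and 6.** State that both primary contrasts use the baseline (pre-valve) HPX-MRI, that follow-up serves to establish EBV success, and that follow-up scans serve the secondary objective.

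**Cost.** No extra scan, reader or participant, since study IDs are already assigned. Reads must be batched or completed before linkage, which may cause a small delay. With about 40 patients at one centre, a reader who attended the MDT may recall a case, so masking may be incomplete.

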### 9.6. Description of study intervention(s), comparators and study procedures (clinical)

This is a prospective, cohort study of patients considered for EBV therapy as part of COPD treatment, using HPX-MRI as an additional imaging test. Please see Appendix A for the study schedule of procedures.

#### 9.6.1. Description of study intervention(s)

#### Hyperpolarised Xenon gas HPX-MRI

HPX-MRI requires breathing in hyperpolarised Xenon, also known as 129Xe. Xenon is an inert gas that is present in the atmosphere in low concentrations, and has no smell or taste. Breathing Xenon or undergoing an MRI scan does not involve exposure to ionising radiation. The Xenon gas is manufactured and released in MHRA regulatory-approved facilities at Oxford. HPX-MR imaging will be performed using Xenon hyperpolarised by a Xenon hyperpolariser, which makes the xenon visible using MRI. The participant will be asked to inhale the gas and to breath-hold for a sufficient time (usually a few seconds) to allow for a successful attainment of images in the MRI scanner. The participant may undergo up to 4 hyperpolarized xenon breath-holds in a single scanning session.

Xenon has been found to be extremely safe and well tolerated, both during single breath-hold experiments. Common side effects include dizziness, drowsiness, deepening of the voice and a feeling of euphoria. They typically last a few seconds. Studies of over 1000 patients performed world-wide have shown no reported serious adverse events related to Xenon inhalation.

The patient will lie in an MR scanner and have conventional safety monitoring throughout the scan. Safety monitoring will consist of a combination of the following: direct visual observation, oxygen saturation and heart rate monitoring.

#### 9.6.2. Description of comparator(s)

There is no comparator in this study.

EXPLICIT Protocol: V1.0 01 Jul 2025

### 9.6.3. Description of study procedure(s)

See Appendix A for Study Schedule for when study procedures are required.

### Clinical information (10 mins)

Medical history including COPD GOLD stage, demographics, smoking and alcohol history, allergies, medications, mMRC dyspnoea scale and anthropometric measurements including height and weight, will be recorded during the study visit and entered directly into the study database.

### Observations (5 mins)

Blood pressure, heart rate, respiratory rate and oxygen saturations

#### 6-minute walk test (10 mins)

A six-minute walk test will be performed if not already performed as part of clinical assessment. The distance achieved (in metres) following 6 minutes of walking will be recorded alongside the pre and post oxygen saturations and mBORG score.

#### Questionnaires (10 mins)

Participant will complete questionnaires addressing dyspnoea and health quality if not already completed as part of clinical work-up (CAT, Dyspnoea-12 and SGRQ). Participants may complete questionnaires using a secure electronic system, either independently via an automated online link or in person with a member of the research team using a tablet device.

Other than recording the severity of physical experience of breathlessness, the Dyspnoea-12 scale also assesses emotional distress with relation to the patient's breathlessness. In cases where the participants score high in this section, the information will be sent further to the concerned clinician for appropriate management of any concerns.

### MRI (approximately 30 mins)

Enrolled participants will be asked to inhale hyperpolarised xenon, on up to 4 occasions per visit (this will enable different sequence data to be acquired, and to allow scanning to be repeated if there is a technical failure).

Xenon is an inert gas that is present in the atmosphere in low concentrations. It has no smell or taste. Breathing xenon or undergoing an MRI scan does not involve exposure to ionising radiation. The xenon gas is manufactured and released in MHRA regulatory approved facilities in Oxford.

